## **12.8. Extension Protocol**

Subjects who remain in the trial until the end of the required Follow-up Period may be eligible to enroll in a separate Extension protocol to continue to receive further mKRAS/mNRAS lymph node immunotherapy to maintain effective levels of antigen-specific T-cells.

## 13. STATISTICS

ELI-002-001 is a multi-center Phase 1 trial to evaluate the safety and efficacy of ELI-002 in subjects with mKRAS/mNRAS solid tumors who have MRD defined as a positive ctDNA blood test or serum tumor biomarkers persisting  $\geq 21$  days post-surgery or after last administration of adjuvant therapy. The investigational product ELI-002 consists of up to 2 amphiphile-modified KRAS peptides plus an amphiphile-modified CpG adjuvant.

Each cohort will be evaluated separately; however, combined analysis of the RP2D and higher dose cohorts may be carried out to improve statistical precision via larger sample size.

### 13.1. Sample Size

Approximately 18 subjects are planned to enroll: 3 to 6 subjects in each of 3 cohorts. The sample size is not based on power calculations, but rather on clinical judgement and the expectation that the objectives of this trial will be met with approximately 18 subjects enrolled in the 3+3 design.

### 13.2. General Statistical Considerations and Definitions

#### 13.2.1. General Statistical Methods

As a general approach, continuous variables will be summarized using mean, standard deviation, median, minimum value, and maximum value. Categorical variables will be summarized using frequency counts and percentages. Time to event data will be summarized using the Kaplan-Meier method. Where appropriate, CIs around point estimates will be presented, and estimates of the median and other quantiles, as well as individual time points (for time to event data) will be produced.

All statistical hypothesis testing within (for change from baseline) and between dose cohorts will be conducted at the 1-sided 0.05 level of significance. Nominal p-values may be computed for secondary or exploratory efficacy analyses as a descriptive measure of strength of results rather than for formal tests of hypotheses. Emphasis will be on RP2D, highest dose, and combined RP2D and all higher doses for change from baseline and comparison to lowest dose. No formal tests of hypotheses are planned for safety analyses.

The following methods will be used in this trial for descriptive summaries and hypothesis testing unless otherwise indicated:

- **Mean change from baseline.** Compared to zero change and compared between dose levels using t-tests from repeated measures as the analysis model and/or via non-parametric tests based on ranks, as appropriate.
- **Median time to event for a single group (non-comparative).** The Kaplan-Meier method will be used to estimate median time to event; 2-sided CIs will use the method of Brookmeyer and Crowley; p-values will not be computed.
- **Hazard ratio of a time to event endpoint comparing two groups.** A stratified Cox proportional hazards model using Efron's method for ties will be used to estimate the HR and 2-sided CI; p-values will be computed using the log rank test.

- **Time to event analysis at a fixed time point.** The Kaplan-Meier method will be used to estimate the survival (or event-free) probability; 2-sided CIs for a single survival probability or for a difference of two survival probabilities will use the complementary log-log method; p-values will be computed using the complementary log-log test statistic.
- **Binary endpoint for a single group (non-comparative).** The binomial parameter (probability of success/failure) will be estimated by the sample proportion. 2-sided CIs will use the method of Clopper and Pearson; p-values will not be computed.
- **Comparison of binary endpoint between two groups.** Difference of sample proportions will be used to estimate the difference in binomial parameters. 2-sided CIs will use Newcombe's score method without continuity correction; p-values will be computed using stratified Cochran-Mantel-Haenszel test.

All descriptive statistical analyses will be performed using SAS statistical software (Version 9.3 or later), unless otherwise noted. Medical History and AEs will be coding using MedDRA.

No adjustment for multiple testing will be made.

### 13.2.2. Analysis Population

The following populations will be used for data analyses and presentations.

#### 13.2.2.1. Full Analysis Set (FAS)

The Full Analysis Set (FAS) will include all subjects who received any amount of ELI-002 vaccine. This population will be used for summaries of subject demographics, and baseline characteristics. Additional exploratory analyses may be performed for the subjects treated at the MTD and doses lower than the MTD at which biomarker (ctDNA, or if ctDNA was not detected at baseline, serum tumor biomarker) clearance/reduction is observed.

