### **13.3.3.2. Analysis of Biomarker Response**

Response will be defined as any subject with a reduction or clearance of biomarker (ctDNA or serum tumor biomarker) compared with baseline [[Tie et al, 2019](#)]. Subjects who do not attain a response for any reason (eg, missing data due to withdrawal) will be counted as non-responders. The subset of subjects with biomarker clearance will also be summarized.

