### 8.1 General Study Design

The Phase 1 study is an open label, single arm, dose-escalation trial incorporating a 3+3 design. Approximately 18 subjects are planned to be enrolled in Phase 1 to evaluate the safety, tolerability and exploratory pharmacodynamic efficacy of subcutaneous ELI-002 using the adjuvant at 3 planned dose levels (Amph-CpG-7909 0.1 mg SC, 0.5 mg SC, 2.5 mg SC) in combination with a fixed dose of Amph-Peptides 2P (700 µg each, for a total of 1.4 mg). Additional cohorts may be added to explore intermediate or higher dose levels based on the cumulative safety review and preliminary review of pharmacodynamic responses. If additional cohorts are added, this will be documented in a study memo sent to all clinical sites and submitted to Institutional Review Boards, per Institutional Review Board guidance.

During the dose escalation study, ELI-002 2P will be comprised of 1.4 mg of two Amph-modified KRAS peptides G12D and G12R admixed with Amph-CpG-7909 to provide ELI-002 2P. Elicio plans to investigate the use of an Amph-Peptide 7P drug product containing all 7 Amph-Peptides (G12D, G12R, G12V, G12A, G12C, G12S, G13D) admixed with Amph-CpG-7909 (ELI-002 7P) in future clinical trials.

Subjects will receive the initial dose of ELI-002 and be monitored for  $\geq 24$  hours after initial dose in order to monitor for potential AEs such as cytokine release syndrome (CRS). In addition, there will be a 1-week stagger between enrollment of the first subject in a cohort and the subsequent subjects. In the absence of toxicity during the dose-limiting toxicity (DLT) assessment window, ELI-002 will be escalated. Planned cohort dose levels are listed below:

- Cohort 1 Dose Level 1: Amph-CpG-7909 0.1 mg with Amph-Peptides 2P
- Cohort 2 Dose Level 2: Amph-CpG-7909 0.5 mg with Amph-Peptides 2P
- Cohort 3 Dose Level 3: Amph-CpG-7909 2.5 mg with Amph-Peptides 2P

Additional cohorts are listed as follows:

- Cohort 4 Dose Level 4: Amph-CpG-7909 5.0 mg with Amph-Peptides 2P

- Cohort 5 Dose Level 5: Amph-CpG-7909 10.0 mg with Amph-Peptides 2P

Cohorts will consist of 3 to 6 subjects (the number will depend on whether DLTs are observed). In order to ensure an adequate number of evaluable subjects, up to 6 subjects may be enrolled per cohort even in the absence of a DLT. Once the RP2D is determined, the cohort evaluating the RP2D Phase 2 dose will be expanded as needed so that there is safety experience with at least 6 subjects at this dose level.

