**Table 8: Derived variables**

Variables	Formula
Demographic and Baseline characteristics	
Body mass index (BMI) (kg/m  )	weight (kg)/[height (m)] 
Derivation of Duration	
Study day at any visit	Date of interest – date of first dose of study treatment. One day is added if this difference is ≥ 0
Duration of study (Days)	(Date of study completion/discontinuation (for discontinued subjects) – date of first dose) + 1
Duration of Exposure to the study treatment ( weeks )	Is [last date of booster dose – first date of immunization dose] + 1] / 7. IF treatment discontinuation, then last date of booster dose = last dose date prior to or at the date of treatment discontinuation.
Treatment Exposure and Compliance	
Cumulative Planned volume (mL)	Total planned volume for each dose* Planned number of doses for the duration of exposure
Cumulative actual volume administered (mL)	Total actual volume administered from exposure CRF page (Cumulative value of 'Actual volume administered' from Study Drug Administration)
Expected Dose	Calculated as the expected number of vaccinations multiplied by assigned dose in mg
Compliance (%)	(Cumulative actual volume administered /Cumulative planned volume)*100
Dose intensity (DI) for ELI-002 Amph-Peptides 2P	Amount of actual cumulative dose of ELI-002 Amph-Peptides 2P (mg) divided by expected dose given for a full 10 course of vaccinations.
Dose intensity (DI) for ELI-002 Amph-CpG-7909	Amount of actual cumulative dose of ELI-002 Amph-CpG-7909 (mg) divided by expected dose given for a full 10 course of vaccinations.
Relative dose intensity	Cumulative dose received divided by expected dose and multiplied by 100
Baseline Derivations	
Baseline value	Unless otherwise specified, the baseline value is defined as the last non-missing observation prior to administration of the first dose of study treatment. For most assessments, this would be the Visit 3 value. If Visit 3 is missing, the Visit 2 value will be used.
Change from baseline	Post baseline value – Baseline value
Fold change from baseline	(Post baseline value – Baseline value)/Baseline value
Biomarker Reduction/Clearance	
Note: All reporting will select the biomarker (ctDNA, CEA, or CA-19) which contains the best (i.e., largest decrease post-baseline) result per subject. If there is no decrease for a given subject, then “best” is the smallest increase.	

**Final Analysis  
Statistical Analysis Plan (SAP)**

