
Clearance
	
Define as the percent change from baseline of the on-study ctDNA, or CA19-9, or CEA that achieved -100%.
 
Notes:
 
 
a. Clearance start will be the date of first clearance.
 
b. Once clearance start date is identified for a biomarker, the same biomarker will be used to determine the clearance end date.
 
c. Results will not be considered if a subject has already started taking subsequent anti-cancer therapy.
 
d. If there is a tie for best response across biomarkers, select ctDNA first.                             
 
▪ For PDAC subjects, select CA19-9 second, CEA third.
 
• For CRC subjects, select CEA second, CA19-9 third.
 
 
 

Reduction
	
Defined as the percent change from baseline of the on-study ctDNA, or CA19-9, or CEA that achieved any decrease (i.e., a negative percent change from baseline).
 
Notes:
 
 
a. Reduction start will be the date of first reduction.
 
b. Once reduction start date is identified for a biomarker, the same biomarker will be used to determine the reduction end date.
 
c. Results will not be considered if a subject has already started taking subsequent anti-cancer therapy.
 
d. If there is a tie for best response across biomarkers, select ctDNA first.                             
 
• For PDAC subjects, select CA19-9 second, CEA third.
 
• For CRC subjects, select CEA second, CA19-9 third.
 
 
 

Duration of Biomarker Clearance/Reduction
	

Clearance Duration
	
This is confirmed after clearance start by an increase above -100% change from baseline followed by a second increase above -100% at least 1 week afterwards.
 
Notes:
 
 
a. The end date will be the date of the first subsequent increase.
 
b. If the increase cannot be confirmed by a second increase, then the potential end date of biomarker clearance will proceed to the next increase and so on.
 
c. Subjects with confirmed clearance duration will not be censored.
 

Reduction Duration
	
This is confirmed after reduction start by an increase above the initial reduction followed by a second increase above the initial reduction at least 1 week afterwards.

**Final Analysis  

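### An optional exploratory subset keeps lower doses only if a biomarker response was seen there, so any response rate drawn from it is biased upward

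*Protocol*

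**What the plan says.** The rule sits in the definition of the Full Analysis Set (FAS), Protocol 13.2.2.1: "Additional exploratory analyses may be performed for the subjects treated at the MTD and doses lower than the MTD at which biomarker" (ctDNA, or a serum marker where ctDNA was not detected at baseline) response has been seen; the clause closes with "serum tumor biomarker) clearance/reduction is observed". SAP 11.1 carries the same sentence. Neither place sets a minimum number of responders, says whether clearance or reduction governs, names the endpoint to be analysed, or says that the retained doses will be pooled.

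Response is defined generously. Protocol 13.3.3.2: "Response will be defined as any subject with a reduction or clearance of biomarker (ctDNA or serum tumor biomarker) compared with baseline". SAP Table 8 counts as reduction any on-study value "that achieved any decrease (i.e., a negative percent change from baseline"), and reports for each subject the marker "which contains the best (i.e., largest decrease post-baseline) result per subject". Clearance in the same table needs a change of -100%, and Protocol 13.3.3.2 summarises it as a separate subset.

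Cohorts are small. Protocol 13.1: "Approximately 18 subjects are planned to enroll: 3 to 6 subjects in each of 3 cohorts". SAP 8.1 adds two dose levels, ending with "Cohort 5 Dose Level 5: Amph-CpG-7909 10.0 mg with Amph-Peptides 2P".

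**The concern.** A lower cohort with no responder leaves the subset and one with a single responder stays, while the MTD cohort stays whatever happens. The data being summarised thus decide who is summarised. With 3 to 6 subjects, a cohort without a responder can easily be chance and need not mean an inactive dose.

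A response rate over the retained cohorts would then exceed the true rate even if every dose worked equally well. Relapse-free or overall survival in the same subset would be tilted in the same direction if responders do better; the documents give no basis for sizing that. SAP 13.1 says the efficacy summaries are there to inform later study designs, so an unlabelled figure from this subset could be carried forward. The subset also has no anchor if no MTD is reached, which the objectives (Protocol 5.1, SAP 7.1.1) allow for.

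**Working it through.** **Plan's own figure.** There is none to reproduce. Protocol 13.1: "The sample size is not based on power calculations, but rather on clinical judgement". Three cohorts of 3 to 6 give 9 to 18 subjects, so the planned 18 is the upper end.

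**Inputs from the documents.** Cohort size 3 to 6; three dose levels (Protocol) or five (SAP); the inclusion rule above, read as at least one responder because no minimum is given.

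**Assumptions, not in the documents.** True response rate *p* from 10% to 70%, equal at all doses; the MTD is the highest dose in the pool; subjects are independent.

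**Formula.** Let the MTD cohort have *M* subjects and let there be *m* lower cohorts of *n*. A lower cohort is dropped with probability q = (1 - p)^n. The number retained, *K*, is Binomial(m, 1 - q). A retained cohort has np/(1 - q) expected responders instead of np. Hence

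E[pooled rate] = Σ P(K = k) × [Mp + k·np/(1 - q)] / (M + kn).

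**Worked case: four lower cohorts of 3, MTD cohort of 6, p = 0.20.** q = 0.8³ = 0.512; Mp = 1.2; np/(1 - q) = 0.6/0.488 = 1.2295.

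| k retained | P(K = k) | Pooled rate |
|---|---|---|
| 0 | 0.0687 | 1.2/6 = 0.2000 |
| 1 | 0.2620 | 2.4295/9 = 0.2699 |
| 2 | 0.3746 | 3.6590/12 = 0.3049 |
| 3 | 0.2380 | 4.8885/15 = 0.3259 |
| 4 | 0.0567 | 6.1180/18 = 0.3399 |

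The weighted sum is 0.296, which is 9.6 points above the true 20%.

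**Expected pooled rate (%) across the range**, agreeing with exact enumeration of all outcomes:

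| Lower cohorts + MTD cohort | p = 10 | p = 20 | p = 30 | p = 50 | p = 70 |
|---|---|---|---|---|---|
| 3 + 6 | 12.4 | 23.4 | 33.4 | 52.1 | 70.6 |
| 3, 3 + 3 | 16.6 | 28.6 | 38.0 | 54.4 | 71.3 |
| 3, 3 + 6 | 14.5 | 26.0 | 35.7 | 53.3 | 71.0 |
| 6, 6 + 6 | 14.5 | 24.0 | 32.5 | 50.5 | 70.0 |
| 3, 3, 3, 3 + 6 | 17.9 | 29.6 | 38.5 | 54.5 | 71.3 |
| 6, 6, 6, 6 + 6 | 16.7 | 25.2 | 33.1 | 50.6 | 70.0 |

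The excess runs from +2.4 to +9.6 points at 10% to 30%, from +0.5 to +4.5 at 50%, and is at most +1.3 at 70%.

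**How often the rule acts.** P(at least one lower cohort dropped) = 1 - (1 - q)^m. For four lower cohorts of 3 this is 99.5%, 94.3%, 81.4%, 41.4% and 10.4% at p = 10, 20, 30, 50 and 70%. For four of 6 it is 95.2%, 70.4%, 39.4%, 6.1% and 0.3%.

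**Without the condition**, the expected pooled rate under equal true rates is Σnp/Σn = p, so the bias is zero.

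**The case against.** The strongest reply is that the text commits to very little. The analysis may be done or not, it is called exploratory, and neither section specifies pooling or a response-rate estimate. The combining that the Protocol does spell out (section 13, opening) follows dose order: the RP2D with higher doses. SAP Table 15 assigns only the FAS. All of this stands, and it makes the inflation conditional on how the subset is used. It does not repair the rule: a subset that may be run after the responding cohorts are known, with no duty to label it, leaves more discretion.

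Second, because any decrease in the best marker counts, the true rate may be high, few cohorts would be dropped, and the bias would be negligible. That also stands if reduction governs. But the clause does not say which of clearance and reduction governs. Clearance can be no more frequent than reduction, and if it governs and is uncommon, the left-hand columns apply.

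Third, the unselected figures are already required: SAP 13.6.1 makes the FAS primary for efficacy, and SAP 13.1 asks for every summary by dose level and overall. This is correct and limits the harm.

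Fourth, equal rates at all doses may be unrealistic in a trial looking for a dose response, and looking further at active doses is a fair descriptive aim. The sizes above do rest on equal rates; the direction does not. Given at least one responder, a cohort's expected observed rate is p/(1 - q) whatever the other doses do: for p = 20%, 0.2/0.488 = 41.0% with 3 subjects and 0.2/0.738 = 27.1% with 6.

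**Conclusion.** The selection rule is faulty and appears in both documents. Any response rate taken over the retained cohorts is biased upward, by about 2 to 10 points if response is infrequent (10% to 30%, plausible if clearance governs), 0.5 to 4.5 points at 50%, and about 1 point or less at 70% or above (plausible if any reduction counts). These sizes assume equal true rates, cohorts of 3 to 6 and a one-responder threshold; the documents give no response rates.

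A reader might infer that the sponsor has planned a pooled response rate that will be materially inflated, or that the trial's efficacy results are compromised. The documents do not support either. The analysis is optional with no stated endpoint or pooling, and the size depends on an unknown rate. The FAS, the secondary endpoint, and the by-cohort and overall summaries do not use the subset.

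**What to change.** In Protocol 13.2.2.1 and SAP 11.1, delete the condition that ends "serum tumor biomarker) clearance/reduction is observed". Any such exploratory analysis then includes all subjects treated at or below the MTD, or at all dose levels tested if there is no MTD, with by-dose results beside it.

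If the sponsor wants to keep a look at the responding doses, label that subset as selected on the outcome, show it next to the all-cohort result, and draw no response-rate estimate from it.

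The cost is one clause in each document, with no change to data collection, dosing or sample size. The exploratory figure may be less favourable, and when there is no MTD it will largely coincide with the overall FAS summary.

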#### 13.2.2.2. Safety Analysis Set

The FAS will be used for the safety evaluation (AEs, clinical laboratory assessments, vital signs, ECGs, ECOG, PEs). No data will be imputed for the safety analysis set; only observed data will be summarized.

#### 13.2.2.3. Disease Response Evaluable Set

All subjects who received any amount of ELI-002 vaccine who have positive MRD at baseline, and either:

1. Have at least 1 available post-baseline MRD assessment, or
2. Have experienced an RFS event (recurrence or death).

This population will be used for supportive analysis of biomarker clearance/reduction and duration of biomarker clearance/reduction.

#### **13.2.2.4. Per Protocol Set**

The Per Protocol Analysis Set will include all FAS subjects who have no major protocol violations. The exclusion list for this set will be identified prior to database lock.

#### **13.2.2.5. PD/Biomarker Evaluable Set**

All Phase 1 subjects who receive any amount of trial treatment, with the additional requirement that relevant blood sampling data at the appropriate assessment time point(s) must be available for inclusion in the analysis for the corresponding parameter.

#### **13.2.3. Missing Data**

There will be no substitutions made to accommodate missing data points unless specifically indicated otherwise. All data recorded on the CRF will be included in data listings that will accompany the clinical trial report.

### **13.3. Statistical Analyses**

#### **13.3.1. Demographic and Background Characteristics**

Demographic and other baseline data, including but not limited to age, sex, race, ethnicity, height, weight, baseline ECOG Performance Status, primary diagnosis, disease stage at diagnosis and screening, and prior therapies (including systemic therapies, radiation, and surgeries, etc.) will be listed individually by subject and summarized by trial phase and treatment group using descriptive statistics (continuous data) or contingency tables (categorical data). The FAS will be used.

#### **13.3.2. Immunogenicity Analysis**

A positive immune response for each KRAS/NRAS peptide will be determined, for example, using a non-parametric distribution-free resampling method for the Fluorospot assay. For all immunogenicity assays, cellular immune responses to ELI-002 will be summarized for each patient by magnitude of response and fold-change from baseline for each timepoint tested. Immune responses will be summarized for each tumor type and dose level cohort.

Statistical tests such as Wilcoxon rank-sum test will be used to compare magnitude of response or changes before and after vaccination when applicable. The p-values associated with these tests will not be used for hypothesis testing.

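### Protocol 13.3.2 gives an independent-samples rank test as its example for before/after immune data that are paired within subject; a paired test should be named (minor)

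*Protocol*

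**What the plan says.** Naming one example of a suitable method, Protocol 13.3.2 (Immunogenicity Analysis) states that the "Wilcoxon rank-sum test will be used to compare magnitude of response or changes before and after vaccination when applicable". The choice is thus left to judgement. The next sentence limits its use: "The p-values associated with these tests will not be used for hypothesis testing".

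Protocol 13.2.1 gives the general approach to mean change from baseline: "Compared to zero change and compared between dose levels using t-tests from repeated measures as the analysis model". Rank methods are allowed there as an alternative or an addition, in general terms only: "via non-parametric tests based on ranks, as appropriate". That approach respects pairing, but it applies only where nothing else is indicated, and its rank test is not named. Where the protocol does test, the general rule is that it "will be conducted at the 1-sided 0.05 level of significance".

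On size, Protocol 13.1 says: "Approximately 18 subjects are planned to enroll: 3 to 6 subjects in each of 3 cohorts". It adds: "The sample size is not based on power calculations".

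The immunogenicity addendum to the SAP takes each subject's Visit 2 sample as baseline (section 1.6) and schedules later samples at Visits 5, 7, 9, 11, 14 and 16 (Table 1-1). It decides response subject by subject (section 2.1) and names neither rank test. SAP 13.1 plans no formal tests. SAP 14.0 drops formal testing except for RFS and OS and refers immunogenicity to the addendum.

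**The concern.** The rank-sum test treats its two columns of values as coming from different people. Here the same people fill both columns. A subject with a high background tends to be high at both times, and a paired analysis removes that variation by differencing. The rank-sum test leaves it in as noise, so with positive correlation its p-value is too large and a consistent rise across subjects can look unremarkable.

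A descriptive p-value still needs a method that fits the data. The protocol assesses pharmacodynamic response through immunogenicity (13.3.6) and defines the RP2D partly on pharmacodynamic data (6.1.1), so a group-level before/after p-value could enter that discussion. Section 13.3.2 is also the only place where a rank test is named for these data, so an analyst asked for a nominal p-value would probably start there.

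**Working it through.** The plan states no power, effect size, SD or within-subject correlation for immunogenicity, so there is no figure of its own to reproduce. Correlation and shift below are assumptions, shown as ranges.

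**Inputs.** About 18 subjects in total and 3 to 6 per cohort (Protocol 13.1). One-sided 0.05 (13.2.1), used only as a reference level. Assumed: before/after values bivariate normal (for example on a log scale) with equal variances, correlation ρ from 0 to 0.7, shift of 0, 0.5 or 1 SD.

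**Direction of the error.** The variance of the mean difference is 2σ²(1−ρ)/n. An independent-samples test acts as if it were 2σ²/n. Its critical value is therefore too strict by a factor of about 1/√(1−ρ). As a normal approximation, the true one-sided level is the upper tail beyond 1.645/√(1−ρ):

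- ρ = 0.3: 1.645/0.837 = 1.97, about 2.5%
- ρ = 0.5: 1.645/0.707 = 2.33, about 1.0%
- ρ = 0.7: 1.645/0.548 = 3.00, about 0.1%

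**Exact tests by simulation, n = 18 (20,000 runs per cell).**

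| ρ | Level under no change, rank-sum / signed-rank | Power at 0.5 SD, rank-sum / signed-rank | Power at 1 SD, rank-sum / signed-rank |
|---|---|---|---|
| 0 | 4.6% / 4.7% | 41.3% / 40.6% | 88.6% / 87.8% |
| 0.3 | 2.6% / 4.9% | 39.4% / 51.6% | 91.9% / 95.4% |
| 0.5 | 1.3% / 5.0% | 38.6% / 62.9% | 95.1% / 99.1% |
| 0.7 | 0.2% / 4.9% | 37.5% / 81.9% | 97.8% / 100.0% |

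The simulated levels agree with the approximation. At 0.5 SD the gap is nil at ρ = 0, then 51.6 − 39.4 = 12.2 points at ρ = 0.3, 62.9 − 38.6 = 24.3 at 0.5, and 81.9 − 37.5 = 44.4 at 0.7. Across simulation runs the signed-rank figure at ρ = 0.5 lies between 63% and 65%. At 1 SD the largest gap is 99.1 − 95.1 = 4.0 points.

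**A full cohort, n = 6.** At 0.5 SD, power goes from 13.6% to 26.6% at ρ = 0.5 and from 10.8% to 36.4% at ρ = 0.7. At 1 SD it goes from 45.3% to 64.4% and from 46.1% to 82.4%. At ρ = 0 the rank-sum test is slightly ahead (44.5% against 40.8% at 1 SD). The small gap at 1 SD is therefore a result for n = 18, not for a single cohort.

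**Smallest attainable one-sided p.** Signed-rank: 1/2ⁿ. Rank-sum: 1/C(2n, n).

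| n | Signed-rank | Rank-sum |
|---|---|---|
| 3 | 1/8 = 0.125 | 1/20 = 0.05 |
| 4 | 1/16 = 0.0625 | 1/70 = 0.014 |
| 5 | 1/32 = 0.031 | 1/252 = 0.004 |
| 6 | 1/64 = 0.016 | 1/924 = 0.001 |

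With 3 or 4 subjects the exact signed-rank test can never reach 0.05. At a 1 SD shift the rank-sum test has about 20% to 26% power there. Ties from values below the limit of quantification were not modelled.

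**The case against.** There is a good case that this hardly matters, and most of it stands.

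- The test is an example, and the sentence can be read as comparing changes between groups, where rank-sum is correct. This stands as a reason for a low rating. It also shows that the sentence needs to separate the two uses.
- Section 13.2.1 already provides for testing change against zero. True, but it gives way where another method is indicated, and its rank test has no name.
- The SAP and its addendum do not specify this test, and the Fluorospot and ICS table shells have no p-value row. This stands: the comparison may never be produced.
- The error is conservative. Under positive correlation the rank-sum test rejects too rarely, so it would not create a false signal.
- At 3 or 4 subjects the replacement performs worse against a 0.05 threshold. This stands and shapes the fix. It is a reason to show individual data at that size rather than to treat pairs as independent.

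A reader might infer that the trial loses much of its ability to show an immune response. The documents do not support that. Response is decided per subject: a two-fold rise over the subject's own baseline, a detectable value after an undetectable baseline, or resampling of Fluorospot wells. None of these uses a rank-sum test. A reader might also take the result at correlation 0.7 as the expected loss. Nothing in the documents fixes the correlation, and it could be low if many baselines fall below quantification.

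**Conclusion.** Minor, but correct as a point of method. For comparing values before and after vaccination in the same subjects, the example in Protocol 13.3.2 is an independent-samples test. Any p-value produced that way ignores the pairing and is too large if the correlation is positive. With 18 pooled subjects and a 0.5 SD shift, the cost ranges from nothing at correlation 0 to about 44 points of power at 0.7; at a 1 SD shift it is about 5 points or less. These figures rest on assumed correlations and shifts, normal data and no ties. The effect stops at descriptive group-level before/after p-values. Responder rates, dose-escalation rules and formal inference are untouched.

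**What to change.** Replace the sentence in 13.3.2 with one that separates the two comparisons:

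- Within subjects, before against after: the exact Wilcoxon signed-rank test, or another test of within-subject change against zero in line with 13.2.1, with a stated rule for ties and values below the limit of quantification.
- Between cohorts: the rank-sum test applied to the changes.

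Apply the signed-rank test to pooled cohorts or to groups of at least 5. For groups of 3 or 4, show each subject's change and give no signed-rank p-value, since it cannot fall below 0.125 or 0.0625. The addendum names neither test today, so it needs the same sentence only if such p-values are added to its outputs.

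The cost is one sentence and a procedure option. No sample, visit or sample-size change is needed.
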